11.4. Vital Sign Measurements

Vital sign measurements, including weight, will be summarized descriptively by visit. In addition, shift tables summarizing the baseline categories (normal, abnormal) versus the category at the end of the respective periods or versus the worst post-baseline category and including subjects who have values at baseline and at least one post-baseline value will be provided. Similarly, in frequency summaries of shifts from baseline at scheduled study weeks per protocol, only subjects who have values at baseline and at the time point will be included. The change from baseline for each of the vital signs including weight will be summarized. A subject data listing of all vital signs and weight data will be provided.

11.5. Physical Examination

A subject data listing of general physical examination will be provided.

CC-10004 (Apremilast)

Statistical Analysis Plan. Protocol CC-10004-PPP-001

12. ANALYSIS FOR COVID-19 IMPACT

The following summary and listing to assess impact of Coronavirus Disease 2019 (COVID-19) will be provided.

- Summary tables showing the number and percentage of subjects with at least one PD and IPD related to COVID-19 and by each category of PD and IPD
- A listing of PD and IPD related to COVID-19
- A listing of treatment-emergent AE related to COVID-19

CC-10004 (Apremilast)

Statistical Analysis Plan. Protocol CC-10004-PPP-001

13.2. Definition of Baseline

Baseline is defined as the value from a sample collected from that subject at the Week 0 randomization visit, prior to dosing of apremilast or placebo.

[figure not shown]
13.3. Baseline Demographic and Disease Background Characteristics

Subject disposition will be provided. Demographic and baseline characteristics will be summarized descriptively by treatment group (placebo and apremilast 30 mg BID) for the [REDACTED] [REDACTED], based on the subjects' randomization assignments. No formal statistical tests will be performed to assess the comparability of the treatment groups at baseline. Descriptive statistics will be provided for the following demographic variables at baseline: age, age category, sex, race, ethnicity, weight and weight category, height, body mass index (BMI), BMI category, and alcohol and tobacco use.

Descriptive statistics will be provided for the following disease background variables at baseline: duration and duration category of PPP; PPPASI total score, PPSI total score, PGA score for palms and soles; prior use of immunosuppressants, colchicines, oral corticosteroids, topical corticosteroids, biologics, non-steroidal anti-inflammatory drugs (NSAIDs), and other analgesics/anesthetics.

CC-10004 (Apremilast)

Statistical Analysis Plan. Protocol CC-10004-PPP-001

CC-10004 (Apremilast)

Statistical Analysis Plan. Protocol CC-10004-PPP-001

14. INTERIM ANALYSIS

No interim analysis is planned prior to the analysis of the primary efficacy endpoint at Week 16.

CC-10004 (Apremilast)

Statistical Analysis Plan. Protocol CC-10004-PPP-001

**15. CHANGES TO THE STATISTICAL ANALYSES SECTION OF
THE PROTOCOL**

No changes to the statistical analyses section of the protocol are made in this SAP.

CC-10004 (Apremilast)

Statistical Analysis Plan. Protocol CC-10004-PPP-001

17. APPENDICES

17.1. Handling of Dates

Dates will be stored as numeric variables in the SAS analysis files and reported in DDMMYY format (ie, the Date9. datetime format in SAS). Dates in the clinical database are classified into the categories of procedure dates, log dates, milestone dates, outcome dates, and special dates.

- **Procedure Dates** are the dates on which given protocol-specified procedure are performed. They include the dates of laboratory testing, physical examinations, etc. They should be present whenever data for a protocol-specified procedure are present and should only be missing when a procedure are marked as NOT DONE in the database. Procedure dates will not be imputed.
- **Log Dates** are dates recorded in CRF data logs. Specifically, they are the start and end dates for adverse events and concomitant medications/procedures. They should not be missing unless an event or medication is marked as *ongoing* in the database. Otherwise, incomplete log dates will be imputed according to the rules in [Section 17.2](#) (eg, for duration or cycle assignment, etc). However, in listings, log dates will be shown as recorded without imputation.
- **Milestone Dates** are dates of protocol milestones such as randomization, study drug start date, study drug termination date, study closure date, etc. They should not be missing if the milestone occurs for a subject. They will not be imputed.
- **Outcome Dates** are dates corresponding to study endpoints such as survival, progression, response etc. In most cases they are derived either from a milestone (eg, the survival date is derived from the death date), a procedure date (eg, the progression date is derived from the date of the tumor scan that was used to determine progression) or an assessment date. They may be subject to endpoint-specific censoring rules if the outcome did not occur, but are not otherwise subject to imputation.
- **Special Dates** cannot be classified in any of the above categories and they include the date of birth. They may be subject to variable-specific censoring and imputation rules.

Dates recorded in comment fields will not be imputed or reported in any specific format.

17.1.1. Calculation Using Dates

Calculations using dates (eg, subject's age or relative day after the first dose of IP) will adhere to the following conventions:

- Study days after the start day of study drug will be calculated as the difference between the date of interest and the first date of dosing of study drug plus 1 day. The generalized calculation algorithm for relative day is the following:
 - If TARGET DATE \geq DSTART then STUDY DAY = (TARGET DATE – DSTART) + 1;

CC-10004 (Apremilast)

Statistical Analysis Plan. Protocol CC-10004-PPP-001

- Else use STUDY DAY = TARGET DATE – DSTART.

Note that Study Day 1 is the first day of treatment of study drug. Negative study days are reflective of observations obtained during the baseline/screening period. Note: Partial dates for the first study drug are not imputed in general. All effort should be made to avoid incomplete study drug start dates.

- Age (expressed in days) is calculated: AGE = CONSENT – DATE of BIRTH + 1. In practice, age will be transformed to years by dividing the difference by 365.25 days, then truncating.
 - Preference is for using calculated age from clinical database. When not available, calculated age from CRF or IVRS may be used
 - Partial birth date: impute missing day as 15th of the month; impute missing month as July; set missing age for missing year
- Intervals that are presented in weeks will be transformed from days to weeks by using (without truncation) the following conversion formula:

$$\text{WEEKS} = \text{DAYS} / 7$$

- Intervals that are presented in months will be transformed from days to months by using (without truncation) the following conversion formula:

$$\text{MONTHS} = \text{DAYS} / 30.4167$$

17.2. Date Imputation Guideline

17.2.1. Adverse Events

Partially missing AE start dates will be imputed in the ADaM dataset for AEs, but partially missing AE end dates will not be imputed in the same dataset. If the AE end date is complete with no missing year, month, or day, and the partially missing start date imputed by the rules below is after the AE end date, then the start date will be imputed by the AE end date.

Subjects who were treated with apremilast at Week 0/Visit 2

The principle of the imputation rules for subjects who were treated with apremilast initially is to treat the AE as treatment-emergent, ie, occurring on or after the date of the first dose of IP, if possible.

Let an AE start date be represented as " $D_{Event}/M_{Event}/Y_{Event}$ ", and the date of the first dose of IP as " $D_{IP}/M_{IP}/Y_{IP}$ ". The following table gives the imputation rules for partially missing AE start dates for subjects who were treated with apremilast initially.

Table 5: Imputation Rules for Partially Missing AE Start Dates for Subjects Who Were Treated with Apremilast Initially

Scenario	Condition	Imputation Rule
	Partially missing date includes year only (both month and day are missing)	

CC-10004 (Apremilast)

Statistical Analysis Plan. Protocol CC-10004-PPP-001

Scenario	Condition	Imputation Rule
1	$Y_{Event} < Y_{IP}$	12/31/ Y_{Event}
2	Otherwise, ie, $Y_{IP} \leq Y_{Event}$	Max (date of first dose of IP, 1/1/ Y_{Event})
Partially missing date includes both year and month (only day is missing)		
1	$Y_{Event} < Y_{IP}$, or ($Y_{Event} = Y_{IP}$ and $M_{Event} < M_{IP}$)	Last date of M_{Event}/Y_{Event}
2	Otherwise, ie, $Y_{IP} < Y_{Event}$, or ($Y_{IP} = Y_{Event}$ and $M_{IP} \leq M_{Event}$)	Max (date of first dose of IP, 1/ M_{Event}/Y_{Event})

Subjects who were treated with placebo at Week 0/Visit 2

The principle of the imputation rules for subjects who were treated with placebo initially and started apremilast treatment at Week 16 is to consider the AE starting on or after the date of the first dose of apremilast, if possible; if the partially missing start date suggests that it is prior to the date of the first dose of apremilast, the AE will be considered starting on or after the date of the first dose of IP, if possible.

The following are 4 scenarios considered in the imputation rules:

1. The partially missing AE start date suggests the date is prior to the date of the first dose of IP: impute it by the latest possible date (determined by the non-missing field of the date);
2. The partially missing AE start date suggests the date is after the date of the first dose of apremilast following Week 16: impute it by the earliest possible date (determined by the non-missing field of the date);
3. The partially missing AE start date is in the same year (if both month and day are missing), or the same year/month (if only day is missing) of the first dose of apremilast following Week 16: impute it by the date of the first dose of apremilast;
4. The partially missing AE start date suggests the date is no earlier than the date of the first dose of IP but prior to the date of the first dose of apremilast following Week 16: impute it by the date of the first dose of IP, or the earliest possible date (determined by the non-missing field of the date), whichever occurs later.

Let an AE start date be represented as " $D_{Event}/M_{Event}/Y_{Event}$ ", the date of the first dose of IP as " $D_{IP}/M_{IP}/Y_{IP}$ ", and the date of the first dose of apremilast following Week 16 as " $D_{APR}/M_{APR}/Y_{APR}$ ". The following table gives the imputation rules for partially missing AE start dates.

Table 6: Imputation Rules for Partially Missing AE Start Dates for Subjects Who Were Treated with Placebo Initially

Scenario	Condition	Imputation Rule
Partially missing date includes year only (both month and day are missing)		
1	$Y_{Event} < Y_{IP}$	12/31/ Y_{Event}
2	$Y_{Event} > Y_{APR}$	1/1/ Y_{Event}

CC-10004 (Apremilast)

Statistical Analysis Plan. Protocol CC-10004-PPP-001

Scenario	Condition	Imputation Rule
3	$Y_{Event} = Y_{APR}$	Date of first dose of apremilast following the early escape
4	Otherwise, ie, $Y_{IP} \leq Y_{Event} < Y_{APR}$	Max (date of first dose of IP, 1/1/ Y_{Event})
Partially missing date includes both year and month (only day is missing)		
1	$Y_{Event} < Y_{IP}$, or ($Y_{Event} = Y_{IP}$ and $M_{Event} < M_{IP}$)	Last date of M_{Event}/Y_{Event}
2	$Y_{Event} > Y_{APR}$, or ($Y_{Event} = Y_{APR}$ and $M_{Event} > M_{APR}$)	$1/M_{Event}/Y_{Event}$
3	$Y_{Event} = Y_{APR}$ and $M_{Event} = M_{APR}$	Date of first dose of apremilast following the early escape
4	Otherwise, ie, $Y_{IP} < Y_{Event} < Y_{APR}$, or ($Y_{IP} = Y_{Event} < Y_{APR}$ and $M_{IP} \leq M_{Event}$), or ($Y_{IP} = Y_{Event} = Y_{APR}$ and $M_{IP} \leq M_{Event} < M_{APR}$), or ($Y_{IP} < Y_{Event} = Y_{APR}$ and $M_{Event} < M_{APR}$)	Max (date of first dose of IP, 1/ M_{Event}/Y_{Event})

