3.2. Secondary Objective

The secondary objective is to evaluate the safety and tolerability of apremilast 30 mg BID compared with placebo in Japanese subjects with PPP.

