11. SAFETY ANALYSIS

Safety analyses will be performed using the safety population. The safety analyses for the placebo-controlled phase will be based on the safety population and presented by treatment group, and the safety analyses for the apremilast-exposure period will be based on the apremilast subjects as treated population and presented by treatment group (Placebo/30 mg BID, 30 mg BID as initiated and 30 mg BID as treated).

For safety analyses in the placebo-controlled phase, baseline will be relative to the first dose date following randomization at Week 0. For safety analyses in apremilast-exposure period, baseline will be relative to the first apremilast dose date at Week 0 for subjects initially randomized to apremilast or Week 16 for subjects initially randomized to placebo and switched to apremilast in the active treatment phase (Weeks 16 to 32).

Unless otherwise specified, the analyses of AEs and marked abnormalities (laboratory parameters and vital signs) for both the placebo-controlled phase and apremilast-exposure period will include the subject incidence rate. To account for the different exposure to the IP, the exposure-adjusted incidence rate will also be presented.

- Subject incidence: Subject incidence (i.e., percentage [%] used in a frequency summary) is defined as the number of subjects with the specific event divided by the number of subjects included in the analysis. Subjects with multiple occurrences of the specific event in the specific phase or analysis period will be counted only once in the numerator. If a subject experiences multiple AEs under the same preferred term (system organ class), then the subject will be counted only once for that preferred term (system organ class).

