11.1. Adverse Events

Adverse events will be analyzed in terms of treatment-emergent adverse events (TEAEs) which are defined as any AEs that begin or worsen on or after the first dose of IP through 28 days after the last dose of IP or study treatment discontinuation date, whichever is later. All AEs will be classified using the Medical Dictionary for Regulatory Activities (MedDRA) classification

CC-10004 (Apremilast)

Statistical Analysis Plan. Protocol CC-10004-PPP-001

system version 21.1 or higher. Unless otherwise specified, AEs will be summarized by system organ class (SOC) and preferred term (PT), with SOCs presented in the standard international order and PTs within SOCs will be presented in descending order of subject incidence.

A treatment-related TEAE is defined as TEAE which was suspected to be related to the study drugs.

AEs and marked abnormalities will be summarized by subject incidence and EAIR for the placebo-controlled phase (Weeks 0 to 16) and for the Apremilast-exposure period. In addition, selected summaries for the active treatment phase (Weeks 16 to 32) and the observational follow-up phase (4 weeks) will be presented.

An overall summary of the following AE categories will be provided.

- TEAE
- TEAE related to study drug
- Severe TEAE
- Serious TEAE
- Serious TEAE Related to Study Drug
- TEAE leading to dose reduction
- TEAE leading to drug interruption
- TEAE leading to drug withdrawal
- TEAE leading to death

In addition, for apremilast-exposure period overall summary of TEAEs will also be provided.

Tables summarizing the incidence of TEAEs by SOP and/or PT will be generated for each of the following:

- All TEAEs
- Most frequent TEAEs (subject incidence $\geq 5\%$ or another cut-off if justified)
- Treatment-related TEAEs
- TEAEs by maximum severity
- Serious TEAEs and treatment-related serious TEAEs
- TEAE leading to dose reduction
- TEAE leading to drug interruption
- TEAE leading to drug withdrawal
- TEAE leading to death
- First onset and new events of TEAE by exposure interval
 - placebo controlled phase (weeks): ≤ 1 , > 1 to ≤ 2 , > 2 to ≤ 4 , > 4 to ≤ 8 , > 8 to ≤ 12 , > 12 to ≤ 16 , > 16

CC-10004 (Apremilast)

Statistical Analysis Plan. Protocol CC-10004-PPP-001

- apremilast-exposure period (weeks): ≤ 1 , > 1 to ≤ 2 , > 2 to ≤ 4 , > 4 to ≤ 8 , > 8 to ≤ 12 , > 12 to ≤ 16 , > 16 to ≤ 24 , > 24 to ≤ 32 , > 32
- TEAE for the subgroups in [Section 10.4](#)

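### Partial AE start dates in the Week 16 switch month or year are imputed into Weeks 0-16 for apremilast but out of Weeks 0-16 for placebo, unless an earlier complete end date intervenes

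*SAP*

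**What the plan says.** SAP 17.2.1 gives one set of rules per initial treatment and describes a single imputed start date in the AE analysis dataset.

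- **Initially apremilast (Table 5).** The aim is to "treat the AE as treatment-emergent, ie, occurring on or after the date of the first dose of IP, if possible". A partial date not before the month or year of first dose becomes the later of the first IP dose and the first day of the known month or year.
- **Initially placebo (Table 6).** Scenarios 1, 2 and 4 give the same dates as Table 5. Scenario 3 does not: when the known month or year is that of the first apremilast dose after Week 16, the text says to "impute it by the date of the first dose of apremilast". The table cell reads "Date of first dose of apremilast following the early escape".
- **Override, both arms.** If the AE end date is complete and falls before the imputed start, the end date is used as the start.

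For safety, SAP 5.2.1 starts the active treatment period on the day of the first apremilast dose in that period, and the footnote to SAP Table 4 does the same for AE data.

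SAP 3.2 sets the secondary objective: to "evaluate the safety and tolerability of apremilast 30 mg BID compared with placebo". SAP Section 11 adds: "The safety analyses for the placebo-controlled phase will be based on the safety population and presented by treatment group". SAP 11.1 reports AEs for that phase as subject incidence and exposure-adjusted incidence rate (EAIR). No separate imputation rule is given for those tables.

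**The concern.** The placebo-arm rule suits the apremilast-exposure tables, where a doubtful event in a subject who has switched is cautiously charged to apremilast. The same imputed date also feeds the Weeks 0-16 tables, where the two randomised groups are compared. There, identical information about an event is handled differently according to arm. Weeks 0-16 is the only period with a concurrent placebo group, so any distortion falls on the one comparison that serves the secondary objective. Tables that inherit the imputed date, such as AEs by exposure interval, carry the same asymmetry.

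**Working it through.** **Inputs.** Tables 5 and 6 and the end-date override (SAP 17.2.1); active-period start (SAP 5.2.1, Table 4 footnote); Week 16 on Day 113, which is 112 days after first dose (SAP Table 4); 43 subjects per arm (Protocol 4.1). The plan states no figure for AE date imputation. Its sample size does reproduce: 45% versus 20%, two-sided 0.10, 80% power gives 43 per arm (power at 43 is 80.5%). It is used here only as a denominator.

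**Worked case.** First dose 24 Feb 2020, Week 16 switch 15 Jun 2020 (Day 113).

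| Recorded start | Initially apremilast | Initially placebo |
|---|---|---|
| Feb 2020 | 24 Feb, Day 1 | 24 Feb, Day 1 |
| May 2020 | 1 May, Day 68 | 1 May, Day 68 |
| Jun 2020 | 1 Jun, Day 99 (Weeks 0-16) | 15 Jun, Day 113 (active phase) |
| Jul 2020 | 1 Jul, Day 129 | 1 Jul, Day 129 |
| 2020 only | 24 Feb, Day 1 (Weeks 0-16) | 15 Jun, Day 113 (active phase) |

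Only the switch-month and switch-year rows differ. If the placebo event recorded as Jun 2020 has a complete end date of 10 Jun, the override dates it 10 Jun (Day 108) and it stays in Weeks 0-16.

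The divergence does not need first dose and switch in the same calendar year. With first dose 2 Nov 2020 and switch 22 Feb 2021, a date giving only 2021 goes to 1 Jan 2021 (Day 61) on apremilast and to 22 Feb 2021 (Day 113) on placebo.

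**Enumeration.** Both tables were applied literally to every first-dose date in a year and every true onset day in Weeks 0-32. Uniform first-dose dates, uniform onset and AE durations of 3 to 28 days are assumptions, not figures from the documents. The percentages below are of partial dates, not of all AEs.

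No usable end date:

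| Missing part | True Weeks 0-16 events kept there: apremilast / placebo | True Weeks 16-32 events moved into Weeks 0-16: apremilast / placebo |
|---|---|---|
| Day | 100% / 86.8% | 13.1% / 0% |
| Month and day | 100% / 15.4% | 84.6% / 0% |

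Hand check of the first row: on average about (30.5 - 1)/2 = 14.75 days of the switch month precede the switch, and 14.75/112 = 13.2%, which leaves 86.8%.

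Complete end date, true Weeks 0-16 placebo events kept:

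| AE duration (days) | 3 | 7 | 14 | 28 |
|---|---|---|---|---|
| Day missing | 97.5% | 94.6% | 90.6% | 86.9% |
| Month and day missing | 97.3% | 93.8% | 87.8% | 76.0% |

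The apremilast figures are unchanged by the end date.

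**Scale.** One reclassified, otherwise event-free subject changes an arm's incidence by 1/43 = 2.3 percentage points. EAIR on apremilast can rise further, because SAP Section 11 stops exposure time at the event start date and an early imputed date shortens it.

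**One rule in both arms.** With the Table 5 rule throughout, the day-missing case without a usable end date gives 1.13 events assigned to Weeks 0-16 per true Weeks 0-16 event in each arm, instead of 1.13 versus 0.87.

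**The case against.** **The effect is narrow and probably small.** This stands. The rules differ only for the switch month or year, the override keeps most short placebo events in place, and SAP 17.1 expects AE dates to be complete unless the event is ongoing. AEs are collected every two weeks to Week 16, so year-only dates should be rare. Safety is descriptive, so no error rate is at stake, though a descriptive difference can still be distorted.

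**The direction is conservative.** This also stands. The rule overstates apremilast risk relative to placebo and cannot hide a harm. It does not make the between-group difference correct.

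**A symmetric rule has its own error.** Placebo subjects start apremilast at Week 16, and Protocol 6.5.5 notes that most post-marketing reports of severe gastrointestinal events arose in the first few weeks of treatment. Switch-month events in that arm may therefore cluster after the switch, and the Table 5 rule would backdate them into the placebo phase. Equal handling of equal dates does not guarantee equal error when onset patterns differ. This is why a sensitivity table is needed.

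**The period boundary is unclear.** SAP 5.2.1 ends the placebo-controlled period on the Visit 10 day, which can be the switch day. The safety start of the active period and the Table 4 footnote resolve this towards the active phase.

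**Stronger readings.** A reader might infer that partial dates in general land wholly in Weeks 0-16 on apremilast and never on placebo. The tables do not support that: the all-or-nothing contrast needs a switch-month or switch-year date, no complete end date before the switch, and a switch that is not on the first day of that month or year. A reader might also put a figure on the total bias in percentage points. The documents give no count of partial dates from which to derive one.

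**Conclusion.** The point holds in this limited form. As written, the plan classifies the same partial date differently by arm when the known month or year contains the Week 16 switch, subject to the end-date override. In the Weeks 0-16 tables this can only add events to apremilast and remove them from placebo. The mechanism and direction follow from the SAP text alone; the percentages rest on uniform entry and onset and the assumed durations. The total effect is unknown and likely small, but with 43 per arm a single subject is visible at 2.3 points. The early-escape wording in Table 6 is editorial: this design has no such feature, and the accompanying text makes clear that the Week 16 switch is meant.

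**What to change.** - For the Weeks 0-16 AE tables, derive the imputed start date by one treatment-independent rule in both arms, for example the Table 5 rule with the end-date override kept.
- Keep the Table 6 rule for a second imputed date that feeds only the apremilast-exposure tables.
- Report the number of ambiguous partial dates by arm. If there are any, add a sensitivity table that places all of them after the switch in both arms, so that the comparison is seen under both assignments.
- Replace the early-escape wording in Table 6 with the Week 16 switch.

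The cost is one extra derived date, one small table and a few lines of SAP text. A few placebo-arm events may appear in both the Weeks 0-16 and the apremilast-exposure tables; a footnote can say so.
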